8.1 Definitions

An adverse event (AE) is defined as an unwanted medical occurrence in a subject. This definition does not imply that there is a relationship between the AE and the device under investigation. This can include, but is not limited to, a change in the subject's health status from baseline that is related to the disease process, interventional procedures, investigational device, and/or side effects to medications.

An adverse device effect is defined as those adverse events that are caused by, or related to, the device.

A serious adverse event (SAE) is an adverse event that led to a death or led to a serious deterioration in the health of a subject that:

1. Resulted in a life-threatening illness or injury,
2. Resulted in a permanent impairment of a body structure or body function,
3. Required in-subject hospitalization or prolongation of existing hospitalization,
4. Resulted in medical or surgical intervention to prevent impairment to body structure or a body function, or
5. Led to fetal distress, fetal death or a congenital abnormality or birth defect.

Each AE will be assessed by the site investigator to determine whether it is serious or non-serious. (Note: Seriousness is different from severity; severity is used to describe the intensity of an event experienced by the subject).

A serious adverse device effect is an adverse event that is both serious and device related.

8.2 Anticipated Adverse Events (AEs)

All expected adverse events are listed in each device's IFU. Potential complications associated with interventional procedures, access, and device are described per each site's

standard of care pre-procedure consenting. Since this observational registry does not include any investigational devices or procedures, anticipated AEs are only specified in the IFUs, not in the protocol.

There may be additional unforeseen adverse events.

8.3 Follow-up of Adverse Events

All device related adverse events observed from the time of enrollment throughout the duration of the study must be reported on the eCRF. All device related adverse events will be followed until resolution or stabilization of symptoms through study completion and/or the subject withdraws consent. Resolution means that the subject has returned to a baseline state of health. Stabilization means that the investigator does not expect any further improvement or worsening of the adverse event.

8.4 Causality Rating

The causal relationship of an adverse event to the device will be rated as follows:

Possible: An event that is unlikely caused by using the device. An alternative explanation - e.g., concomitant drug(s), concomitant disease(s) - is inconclusive. The relationship in time is reasonable; therefore, the causal relationship cannot be excluded.

Probable: An event that might be due to the use of the device. An alternative explanation is less likely - e.g., concomitant drug(s), concomitant disease(s). The relationship in time is suggestive of a direct relationship to the device.

Definitely: An event that is attributed to the use of the device. The event cannot be reasonably explained by an alternative explanation - e.g., concomitant drug(s), concomitant disease(s).

8.5 Severity of Adverse Events

The severity of adverse events will be rated as follows:

Mild	An adverse event that is tolerated by the subject, causes minimal discomfort and does not interfere with everyday activities, does not need medical treatment or intervention.
Moderate	An adverse event that is sufficiently discomforting to interfere with normal everyday activities; intervention may or may not be needed.
Severe	An adverse event that prevents normal everyday activities; treatment or other intervention usually needed.

8.6 Adverse Event Monitoring

Adverse events will be reviewed and assessed by the principal investigator at each site.

Treatment for adverse events will be per standard of care as determined by the site investigator. Device related adverse events reported in the eCRF will be processed in the standard compliant fashion for the manufacturer.

9 Risk Assessment

9.1 Risk Management Procedure

Subjects will be monitored for the duration of the study. Risks will be mitigated through selection of qualified physicians, appropriate training, and study monitoring ensured by the following:

- Investigators who participate in the study will be experienced and skilled in radial access for visceral interventions. Additionally, investigators, in conjunction with the investigational site, will have adequate resources for participation in a registry study.
- Each investigator will ensure oversight and approval of the study by their IRB/EC prior to initiation of the study at their site.
- The investigator and study personnel will be trained on the study protocol.
- Subjects will be carefully evaluated against the eligibility criteria prior to entering the study to ensure that their diagnosis and medical status are appropriate for participation.

- Subjects will be monitored throughout the follow-up period as defined in the study protocol. Subjects will have visits with the investigator or designee to review the subjects' status.

9.2 Potential Benefits

Subjects enrolled in this clinical study will be monitored closely throughout the study and have regular assessments according to the investigator's standards of care. The data collected during the clinical study will provide further understanding of procedural and technical success of radial access for HydroPearl procedures.

10 Monitoring

Data will be collected using eCRFs for this study. Sites will enter data directly into the eCRFs via a web-based system. Sponsor representatives (study monitors) will schedule periodic, on-site visits to review source data and compare to eCRFs.

Study monitors will work in accordance with Sponsor standard operating procedures (SOPs) and the Study Monitoring Plan.

At the site, monitors will perform and verify the following:

- The adequacy and experience of the study center including Sponsor notification of any problems relating to facilities, technical equipment or medical staff
- Written Informed Consent has been obtained from all subjects prior to any study related procedures being performed and that data is recorded correctly and completely
- Source Document Verification (SDV): comparing data in the eCRFs to ensure they correspond with applicable source data, and to inform the Sponsor and investigator of any discrepancies, errors or omissions
- Ensure adherence to the protocol and applicable regulations at the site and notify the Sponsor promptly of any deviations
- Evaluate subject compliance and support subject retention efforts at the site

11 Image Analysis

Imaging, if completed, will be analyzed per standard of care at each site and results reported in eCRF; however, images will not be collected nor archived by the Sponsor.

12 Device Failure and Malfunction

A device failure has occurred when the device is used in accordance with the IFU, but does not perform as described in the IFU, and negatively impacts treatment of the study subject.

13 Statistical Methods

13.1 Sample Size Determination

. This observational study is not testing a hypothesis; therefore, no power calculations were completed. The stated sample size will provide a reasonable assimilation of safety of the device and will allow detection of rare major complication with a reasonable probability. That is, a sample size of 100 evaluable patients would provide greater than 80% probability of observing 1 or more major complications that may occur at a population rate of 1.6% or more.

13.2 General Considerations

Evaluations will be reported with descriptive statistics including 95% confidence intervals. Continuous endpoints will report the mean and standard error, median, min, and maximum values. Categorical endpoints will be summarized by proportion of each category. Time-to-event endpoints will be summarized via Kaplan-Meier survival analyses, along with median and associated 95% interval. The associated Kaplan-Meier curves will be displayed as appropriate.

Sub-group analyses include, but are not limited to:

- UFE treatment procedure
- Hypervascular benign and malignant liver treatment procedures
- AVM procedures
- PAE treatment procedure

13.2.1 Study Visit

The Study Visit Day 0 is the date of the index procedure. Day in study will be calculated relative to the index procedure as follows:

$$\text{Study Day} = \text{Assessment Date} - \text{Index Procedure Date}$$

For each subject, duration in study will be based on last study contact date which is the latest date of all follow-up visits, assessments, adverse event onset or resolution, and study exit including date of death.

Duration variables will be calculated as follows:

$$\text{Duration Days} = \text{End Date} - \text{Start Date}$$

13.2.2 Visit Windows

Unless otherwise specified, visit assessments will be analyzed for each analysis time point according to the visit entered in the eCRF.

13.3 Analysis Populations

Analyses for primary and secondary evaluations will be based on the Primary Analysis Set, defined as all enrolled subjects (i.e., those who signed the informed consent form and meet all protocol eligibility criteria) who are treated.

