3.2.1 Primary Evaluations

Primary Safety Evaluation:

The primary safety evaluation is freedom from major adverse events and radial access complications within 30 days post-procedure.

Major Adverse Events are defined as:

1. Death
2. MI
3. Stroke

Radial Access related complications are defined as:

1. Radial artery occlusion
2. Hand ischemia
3. Arteriovenous fistula
4. Pseudoaneurysm
5. Any complication requiring surgical and/or endovascular intervention within 30 days of index procedure.

Primary Efficacy Evaluation:

The primary efficacy evaluations are procedural success and technical success.

1. Procedural success is defined as completing the planned procedure without femoral access bailout.
2. Technical success is defined as delivery of HydroPearl to the target vessel and slowing the blood flow with microsphere embolization. Embolization may be confirmed clinically or radiologically at the discretion of the site investigator.

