3.2.2 Additional Evaluations

Additional evaluations include:

1. Incidence of Radial Artery Occlusion Complications at any time
 - a. Arteritis
 - b. Cellulitis
 - c. Ecchymosis
 - d. Pain at puncture site
 - e. Hematoma

2. Quality of Life and health economics
3. Post embolization syndrome
4. Procedural endpoints:
 - a. Blood loss
 - b. Patient radiation exposure
 - c. Contrast volume
 - d. Time to hemostasis
 - e. Total procedural time
 - f. Time to discharge
 - g. Operative time
5. Access endpoints:
 - a. Radial artery spasm,
 - b. Time to discharge
6. Closure endpoints
 - a. Time to hemostasis
 - b. Time to ambulation
7. Tumor type
8. Number and size of tumors / fibroids
9. Post embolization syndrome
10. UFE:
 - a. If post-op MRI is obtained per standard of care: Effectiveness of HydroPearl measured by MRI.
 - i. Infarction is characterized by complete (100%), 90-99%, 50-89%, or less than 50%.
 - ii. Uterine Volume
 - iii. Dominant Fibroid Volume
 - b. EQ-5D
 - c. UFS-QoL
 - d. Return to normal activities
 - e. Pain VAS
 - f. Symptoms including bleeding and bulk
 - g. Pregnancy intention and occurrence
11. PAE:
 - a. IPSS with Quality of Life

- b. EQ-5D
- c. Return to normal activities
- d. Pain VAS
- e. Qmax
- f. Prostate volume

12. Liver Tumor Embolization:

- a. Tumor response (mRECIST - CR, PR, SD, PD)
- b. EQ-5D
- c. Return to normal activities
- d. Pain VAS
- e. Disease stage

13. Other Hypervascular Tumors

- a. Infarction
- b. Tumor Response (mRECIST – CR, PR, SD, PD)
- c. Return to normal activities
- d. Pain VAS

14. Arteriovenous malformations:

- a. EQ-5D
- b. Return to normal activities
- c. Pain VAS

4 Study Design

This is a prospective, multi-center, registry study to assess the procedural success, technical success, and complication rate of radial access procedures using HydroPearl microspheres.

A subject is considered enrolled into the study once the guidewire is inserted into the radial artery.

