4.1.2 Exclusion Criteria

Subjects will not be permitted to participate in the study if they meet any of the following exclusion criteria:

1. Unable to have a procedure with radial access for any reason.
2. Participating in another clinical study which, in the opinion of the investigator, could impact the results of this registry.
3. Pregnant or planning to become pregnant during the study.

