7.1 Screening/ Baseline Visit

Prior to the procedure, subjects must sign the informed consent form, meet all the inclusion and none of the exclusion criteria. The screening visit will follow each study site's standard of care and typically consists of a review of medical history and demographics, blood tests, imaging, review of concomitant medications, and pregnancy test if appropriate.

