7.7 Clinical Data Collection

Information about subject demographics, eligibility requirements, procedure, specific concomitant medications as well as complications and/or device related adverse events will be collected on the eCRFs provided by the Sponsor. The eCRFs should accurately reflect data contained in the subject's medical records (i.e. source documents).

8 Adverse Events

Subject complications will be monitored via the reporting of device related adverse events occurring from the time of enrollment (insertion of guidewire into radial artery) through study completion (withdrawal for any reason or completion of 365-day follow-up visit). For this registry, adverse events collected will be limited to any events possibly, probably or definitely related to a Terumo device, as described below in Section 8.2.

Where an adverse event has, by its nature, a prolonged course, the event will be considered a single event and not multiple events.

The investigator is not required to actively seek adverse events from a subject once a subject has exited the study. If the investigator learns of any device related adverse event at

any time after a subject's exit from the study, the investigator should promptly report it to the Sponsor.

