13.6 Subject Disposition

Subjects who sign an informed consent form, but do not meet all protocol eligibility criteria (i.e., screening failure), will be excluded from the statistical analyses.

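### 'Enrolled' has two definitions and 'treated' has none, so the procedural-success denominator is not fixed for a radial access that fails before any guidewire enters the artery

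*Combined protocol and SAP*

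**What the plan says.** Section 13.3 uses a single Primary Analysis Set for the primary and secondary evaluations, "defined as all enrolled subjects (i.e., those who signed the informed consent form and meet all protocol eligibility criteria) who are treated". Its gloss on *enrolled* is consent plus eligibility.

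Section 4 gives a different rule: "A subject is considered enrolled into the study once the guidewire is inserted into the radial artery". Section 8 repeats it when it sets the window for device-related adverse events, which are those "occurring from the time of enrollment (insertion of guidewire into radial artery) through study completion".

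The two primary efficacy evaluations are in section 3.2.1. "Procedural success is defined as completing the planned procedure without femoral access bailout", and "Technical success is defined as delivery of HydroPearl to the target vessel and slowing the blood flow with microsphere embolization". The second does not mention the access route.

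*Treated* is not defined anywhere. Inclusion criterion 2 (section 4.1.1) refers to treatment with HydroPearl, and section 13.2 uses the word in subgroup labels. Neither says whether an attempted procedure, a femoral delivery or only a radial delivery counts.

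The target population is described by intention in the synopsis (procedures planned by radial access) and in section 2.2 (subjects scheduled for them). The objective, in the synopsis and section 3.1, speaks instead of patients undergoing embolization via radial access.

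**The concern.** Procedural success by the radial route is part of the stated objective, and its failures are access failures. A subject in whom the radial artery cannot be entered, and who is embolized from the groin, is the kind of case this evaluation exists to count. Whether that subject is counted depends on which definition of *enrolled* the analyst applies, and no section says which one governs. Two analysts following the plan could therefore report different denominators from the same data.

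The undefined *treated* adds a second filter, applied after the procedure has begun. If it were read as HydroPearl delivered, which is a possible reading but not a stated one, abandoned procedures and non-deliveries would also leave the set, and the delivery part of technical success would be met by construction.

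**Working it through.** **1. The plan's own figure.** Section 13.1 states a probability above 80% of seeing at least one major complication with 100 evaluable patients at a rate of 1.6%. The formula is 1 - (1 - 0.016)^n.
- n = 100: 80.07%, so the statement reproduces.
- n = 99: 79.75%. n = 98: 79.42%.
- Smallest n for 80%: ln(0.2)/ln(0.984) = 99.78, so 100.

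The statement is correct but has no slack, so it matters who counts among the 100.

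**2. The two rules side by side.** All subjects below are consented and eligible.

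| What happens | 13.3, consent plus eligibility | Sections 4 and 8, guidewire rule |
|---|---|---|
| No wire enters the radial artery; embolized femorally | In, procedural failure, if *treated* includes femoral delivery; can still be a technical success | Not enrolled; in no primary denominator |
| No wire enters; procedure abandoned | Out, unless *treated* means attempted | Not enrolled |
| Wire enters; femoral bailout; embolized | In, procedural failure, on the same condition | Enrolled; then as under 13.3 |
| Wire enters; no HydroPearl delivered | Depends on *treated* | Enrolled; then depends on *treated* |
| HydroPearl delivered radially; flow not slowed | In, technical failure | In, technical failure |

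The enrollment conflict bites only in the first two rows. In the second row the subject may be absent under both rules. The *treated* gap also affects the third and fourth rows.

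**3. Direction for procedural success.** Per 100 attempts, let k be the failures before any wire entry and r the other counted procedural failures. Counting everyone gives (100 - k - r)/100. The guidewire rule gives (100 - k - r)/(100 - k). The ratio of the second to the first is 100/(100 - k), which is never below 1.

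**4. Scale.** The documents give no count of pre-wire failures. In section 1, the cited radial series report success of 97.7% to 100%. The largest reports 27 crossovers in 1,512 procedures, 27/1,512 = 1.8%, not split at wiring. If that rate applied here and all crossovers were pre-wire, k would be about 2 per 100. I therefore take k from 0 to 3 as an assumption. Intervals are exact (Clopper-Pearson) 95%; when x = n the lower limit is 0.025^(1/n), for example 0.025^(1/98) = 96.3%.

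| k | r | All attempts | Guidewire rule |
|---|---|---|---|
| 0 | 0 | 100/100 (96.4-100%) | 100/100 (96.4-100%) |
| 1 | 0 | 99/100 (94.6-100.0%) | 99/99 (96.3-100%) |
| 2 | 0 | 98/100 (93.0-99.8%) | 98/98 (96.3-100%) |
| 3 | 0 | 97/100 (91.5-99.4%) | 97/97 (96.3-100%) |
| 2 | 2 | 96/100 (90.1-98.9%) | 96/98 = 98.0% (92.8-99.8%) |

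**5. Technical success and safety, k = 2 (assumed).**
- Technical success, with two technical failures among wired subjects and both pre-wire subjects embolized successfully by the femoral route: 98/100 = 98.00% becomes 96/98 = 97.96%, a change of -0.04 points.
- Safety, with two wired subjects having an event: the change is again -0.04 points if neither pre-wire subject has an event. If one does, 97/100 becomes 96/98, a change of +0.96 points.

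**The case against.** The best defence is that the guidewire rule, stated twice, defines a coherent population: radial procedures actually begun. The objective's wording about patients undergoing embolization via radial access fits it. Success given wire entry is then a different quantity, not a biased one. This stands in part. A reader might infer that procedural success is simply biased upward, but that holds only against the planned or scheduled population of the synopsis and section 2.2. The documents support either target and do not choose between them.

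The affected group is also narrow. A wire that enters but cannot be advanced has already triggered enrollment, so only failures before any wire entry are at issue. Section 9.1 requires investigators experienced in radial access, and most cited series report 100% success, so k may be zero. Section 13.7 rules out formal hypothesis tests. All of this stands and limits the weight of the point.

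It could be said that 13.3 governs the analysis and settles the matter. It does not: it leaves *treated* undefined, and it reuses a term that section 4 has already defined differently.

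Three stronger inferences are not supported:
- A reader might combine exclusion criterion 1, "Unable to have a procedure with radial access for any reason", with section 13.6, under which consented subjects who "do not meet all protocol eligibility criteria (i.e., screening failure), will be excluded from the statistical analyses", and infer that a failed attempt can be relabelled a screening failure. Section 7.1 answers this: "Prior to the procedure, subjects must sign the informed consent form, meet all the inclusion and none of the exclusion criteria". Eligibility is settled before the attempt.
- A reader might infer that technical success is 100% by construction. That needs an unstated reading of *treated*, and even then only the delivery part is automatic; slowing of flow can still fail.
- A reader might infer that the sample size statement is wrong. It reproduces.

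Finally, a set based on attempted access appears in neither section 4 nor 13.3, and consistent wording alone would remove the contradiction. That is so. The attempted-access denominator is still worth having, because it is cheap and less open to selection on the outcome.

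**Conclusion.** The point holds as a conflict between stated rules for the primary denominator, together with one undefined term that filters every primary evaluation. It should be fixed, but it does not undermine the registry.

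Confidence is high on the textual conflict and low on its size. Against the planned-radial population, the guidewire rule can only raise procedural success. With an assumed 2 pre-wire failures per 100 attempts and no other failures, the estimate moves by 2 points and its lower limit from 93.0% to 96.3%; with none, nothing moves. The effect on technical success and safety is small in the examples and can go either way. No formal decision depends on it, but the estimates and their intervals are what the registry will report, so the denominator should be settled before analysis.

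**What to change.** - Use one definition of *enrolled* in sections 4, 8 and 13.3. Section 8 ties the start of event collection to enrollment, so its wording must follow the definition chosen.
- Define *treated* in 13.3, stating whether femoral delivery and abandoned procedures count.
- Report procedural and technical success on all consented, eligible subjects in whom radial access was attempted. Count failed radial access, femoral conversion and abandonment as procedural failures, and non-delivery as technical failure.
- Keep the treated set for safety, quality of life and organ-specific outcomes.
- Add a disposition table: attempted, wired, converted to femoral, HydroPearl delivered, abandoned.
- In 13.1, state whether failed attempts count toward the 100 evaluable patients, because the stated probability falls below 80% at 99. If the 100 are counted at guidewire insertion, pre-wire failures use no places; if they are counted earlier, the statement needs rewording.

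The cost is wording in the combined protocol and SAP, one table and a short eCRF record for failed attempts. Reported success may be slightly lower.
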